*Moderated Blood Flow Restriction after Anterior
Cruciate Ligament Reconstruction*

Identifiers: NCT02911909

Unique Protocol ID: 2004255

Date: 06-14-2019

Date: 06-14-2019
Version Number: 3.1
Principal Investigator: [name], DVM, PhD, OTSC
Application Number: 2004255
Application Title: Moderated blood flow restriction after anterior cruciate ligament reconstruction

Moderated Blood Flow Restriction after Anterior Cruciate Ligament Reconstruction

Principal Investigator: [name], DVM, PhD, OTSC
Department of Orthopaedics
[name]
Email: [contact]
[contact]

Coordinating Site: University of Missouri, Missouri Orthopaedic Institute

Funding: Department of Orthopaedic Surgery, University of Missouri

Hypothesis- Patients in the moderated blood flow (Delfi) restriction group will have significantly increased muscle strength, thigh circumference, HGH and IGF levels, and no significant differences in knee range of motion, Lachman exam, KT2000, IKDC, Tegner, PROMIS surveys, VAS scores, or CK levels compared with standard ACL rehabilitation patients.

Background:

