- a. The study will be a prospective, randomized, controlled trial between two treatment cohorts. A total of 50 patients will be enrolled in the study. Informed consent will be obtained in clinic or by phone (Patient IQ e-consent) prior to any surgical intervention, per the IRB protocol. Enrollees will receive a copy of the consent and HIPAA form. All patients that meet inclusion criteria who consent to participate in the study will then be randomly assigned to either the control group or moderated blood flow therapy group. Randomization will occur by autogenerated permuted 1:1 block randomization using electronic assignment from the orthopaedic research team prior to initiation of post-operative therapy. The control group will undergo standard of care, post-operative ACL reconstruction rehabilitation. The treatment group will also receive standard ACL rehabilitation combined with Delfi moderated blood flow restriction therapy. Patients will follow up at standard of care clinic visits and participate in the same standard of care physical therapy protocol for ACL reconstruction. Baseline measurements of thigh circumference, knee ROM, KT 2000, Lachman exam, and labs for HGH, IGF, and CK will be obtained preoperatively. Patients will also complete preoperative IKDC, Tegner, PROMIS, and VAS pain surveys. Measurements of thigh circumference and knee range of motion will occur at 2 week intervals post operatively. Strength testing will start at 6 weeks post-operatively. These measurements will occur during standard therapy sessions. KT 2000 and Lachman exam will be performed at 4, 6, 8, and 12 months post operatively. A standard functional return to sport evaluation will be performed at the 4, 6, 8, and 12 month postoperative visits. Labs for HGH, IGF, and CK will be drawn at 2, 6, 12, and 24 weeks. VAS pain scores will be recorded before and after each therapy session. The PROMIS, IKDC, and Tegner surveys will be given at 4, 6, 8, 12 month intervals. The study will conclude at 12 month follow up. All post-operative visits will be standard of care. No additional clinic visits will be required for this study. Background patient information will be collected including age, sex, BMI, and co-morbidities.
- b. The control group will be necessary to provide a baseline measure on which moderated blood flow therapy will be compared.

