- c. Blinding of the subject will not be possible as the patient will be able to recognize if they have or have not had the moderated blood flow (Delfi) device applied during therapy and application of a sham-device is not practical or considered standard of care. Evaluators performing measurements will be blinded to the patient’s treatment group during assessment of muscle strength, thigh circumference, knee range of motion, Lachman exam, and KT2000. Surgeons will also be blinded to the respective treatment groups. All other outcome measures are objective and quantitative.

Pre-Trial	Investigator discusses study with the patient in person or by phone and provides the patient with a patient Consent Form (in person or electronic)
-----------	--

	Patient provides written consent or electronic consent (Patient IE e-consent) to participate in the study (randomization occurs) IKDC, Tegner, PROMIS, VAS surveys completed. Baseline thigh circumference, ROM, Lachman exam, KT2000 performed Baseline HGH, IGF, CK labs obtained
Day 0	Operative procedure: Documentation of the type of ACL graft used.
Post op Day 1-completion of PT	Patients begin standard physical therapy routine +/- moderated blood flow Thigh circumference, and knee ROM performed every 2 weeks. VAS pain survey recorded before and after each therapy session
Post Op Weeks: 2, 6, 12, 24	Labs for HGH, IGF, and CK levels obtained. Strength testing during routine Physical Therapy visits begins at 6 weeks
4 months post-operatively	Functional return to sport evaluation performed by Physical Therapy IKDC, Tegner, PROMIS, VAS surveys completed. Lachman exam and KT2000 performed.
6 months post-operatively	Functional return to sport evaluation performed by Physical Therapy* IKDC, Tegner, PROMIS, VAS surveys completed. Lachman exam and KT2000 performed.
8 months post-operatively*	Functional return to sport evaluation performed by Physical Therapy IKDC, Tegner, PROMIS, VAS surveys completed. Lachman exam and KT2000 performed.
12 months post-operatively	Functional return to sport evaluation performed by Physical Therapy* IKDC, Tegner, PROMIS, VAS surveys completed. Lachman exam and KT2000 performed Patient will be released from all study activities after the 12 month follow-up visit
* If received as standard of care, data will be collected. If not, data will not be collected	

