All subject information in electronic format will be kept in password-protected storage. All subject information in paper format will be kept in locked cabinets in a secured suite at the Missouri Orthopedic Institute or destroyed.

b. There is potential risk of discomfort from application of the pneumatic tourniquets. This is temporary and occurs during the therapy sessions.

c. Due to the venous pooling from vascular constriction, there is a theoretical risk of increased incidence of blood clots, vascular insufficiency, potential muscle injury, oxidative stress, and possible nerve conduction problems. These theoretical risks have not been demonstrated in previous studies specifically investigating the safety of occlusive therapy (10,11).

5. Benefits

a. There is a potential benefit to the moderated blood flow group of increased muscle mass, strength, and ability to progress in therapy at an accelerated rate compared with control patients. If this benefit is found in the treatment group, moderated blood flow therapy may be able to be used in all ACL reconstruction patients. The hope is that the increased strength and muscle mass will allow patients to progress in therapy at a safe and accelerated rate, and therefore allow patients to get back to their preinjury activities. Otherwise, there are no further direct benefits to the patient for participation in the study.

6. Payment and Remuneration

a. No compensation for participation in the study.

7. Costs

a. Patients that choose to participate in the study will not incur any additional costs related to the study. Patients will receive the standard of care surgical procedure and postoperative rehabilitation protocols. Any additional lab tests and study related measurements will be at no charge to the patient and will be covered by the Department of Orthopaedic Surgery.

8. References

(1)Griffin, Letha Y., et al. "Noncontact anterior cruciate ligament injuries: risk factors and prevention strategies." *Journal of the American Academy of Orthopaedic Surgeons* 8.3 (2000): 141-150.

(2) Iwasa, J., Y. Shima, and L. Engebretsen. "Results of ACL reconstruction." *The Knee Joint*. Springer Paris, 2012. 245-262.

(3) Palmieri-Smith, Riann M., Abbey C. Thomas, and Edward M. Wojtys. "Maximizing quadriceps strength after ACL reconstruction." *Clinics in sports medicine* 27.3 (2008): 405-424.

(4) KAATSU-In Layman's Terms. <http://www.kaatsu-global.com/kaatsu-in-laymans-terms/> Accessed 11/9/15.

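### VAS pain around therapy is scored before and after sessions but not during them, so a null result cannot show that the cuff adds no pain while it is on

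*Combined protocol and SAP*

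**What the plan says.** Study Procedures, item a, sets the timing: "VAS pain scores will be recorded before and after each therapy session". The schedule table, in the row that runs from postoperative day 1 to the end of physical therapy, gives the same timing: "VAS pain survey recorded before and after each therapy session".

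Section 4 (Risks), item b, reads: "There is potential risk of discomfort from application of the pneumatic tourniquets. This is temporary and occurs during the therapy sessions". Item c then lists clots, vascular, muscle, oxidative and nerve effects, and calls these theoretical.

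The Hypothesis puts the VAS among the outcomes expected to show no significant difference: "VAS scores, or CK levels compared with standard ACL rehabilitation patients". The Background repeats that expectation. Section 3, item b, lists VAS pain as a secondary outcome.

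The VAS is also taken away from therapy sessions. Study Procedures, item a, has a preoperative reading: "Patients will also complete preoperative IKDC, Tegner, PROMIS, and VAS pain surveys". The schedule table lists "IKDC, Tegner, PROMIS, VAS surveys completed" at 4, 6, 8 and 12 months; the 8-month row is footnoted as collected only if it is standard of care.

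**The concern.** The cuff is used in one arm only, and the protocol itself says when its discomfort occurs. That period lies between the two session readings. The first reading precedes that session's cuff use. The second follows it, at an unstated interval, and the discomfort is described as short-lived.

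The predicted VAS result is the absence of a difference. Timing that may skip the period of exposure pushes the comparison towards that prediction. If the arms look alike, two explanations remain: the cuff adds little pain, or it adds pain that had faded before anyone asked. The planned data cannot separate them. A report could then present the VAS result as evidence that therapy with the cuff is no more painful, when pain with the cuff inflated was never scored.

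**Working it through.** **Step 1: set the timing side by side.**

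| Moment | VAS scheduled? | Cuff discomfort, as the protocol describes it |
|---|---|---|
| Before surgery | Yes | None: cuff not yet used |
| Before a session | Yes | Precedes that session's cuff use |
| During a session | No | Placed here (section 4, item b) |
| After a session | Yes | Described as temporary; share remaining not stated |
| 4, 6, 8, 12 months | Yes (8 months only if standard of care) | Not a within-session reading |

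No reading falls in the row where the discomfort is placed. Nothing else described in the protocol fills that row. Adverse events are mentioned only for subjects who discontinue (Withdrawal of Subjects), and no other in-session pain score appears.

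**Step 2: the plan's own figure.** No stated number is in dispute here. Section 3, item c, gives 20 per group from a t-test at power 0.8 and alpha 0.05, raised to 25 for loss to follow-up. The 20 cannot be reproduced, because no effect size, SD or sidedness is given. Solved backwards with a two-sided t-test, 20 per group corresponds to a standardised difference of 0.909. The step to 25 fits 20% loss: 20/(1 − 0.20) = 25. These figures only anchor the illustration below; the protocol does not say that the power analysis concerned the VAS.

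**Step 3: how much could be lost (illustration).** Let D be the in-session difference between arms in SD units, and f the share of it still reported at the post-session reading. The documents give neither, so both are assumed. SD units are used because the VAS scale is not stated. With one reading per patient, equal SDs and a two-sided t-test at 0.05, the post-session comparison has

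- degrees of freedom 2n − 2,
- noncentrality f × D × √(n/2).

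For D = 0.9 and n = 20, √(20/2) = 3.162. The noncentrality is 0.9 × 3.162 = 2.85 at f = 1, 1.42 at f = 0.5, 0.71 at f = 0.25 and 0 at f = 0. Resulting power, shown as 20 / 25 per group:

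| D | f = 1 | f = 0.5 | f = 0.25 | f = 0 |
|---|---|---|---|---|
| 0.5 | 0.338 / 0.410 | 0.120 / 0.139 | 0.067 / 0.072 | 0.05 / 0.05 |
| 0.9 | 0.792 / 0.877 | 0.284 / 0.345 | 0.107 / 0.122 | 0.05 / 0.05 |
| 1.2 | 0.959 / 0.986 | 0.456 / 0.547 | 0.152 / 0.180 | 0.05 / 0.05 |

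**Step 4: reading the table.** The result is driven by f. At f = 0 a difference is found only at the false-positive rate, however large D is. At f = 1 nothing is lost. Combining readings over many sessions would change the SD, and so the middle columns. It would not help at f = 0, where no signal is left to average.

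**The case against.** The best defence is that the protocol never calls the VAS a tolerability measure and never says it will conclude that the cuff is painless. The VAS sits beside range of motion, Lachman, KT2000 and the functional scores. Whether sessions with added restriction leave the knee more painful is a coherent question, and before and after readings address it. This stands, and it limits the point to what may be claimed from the VAS.

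A reader might also infer stronger things, which the documents do not support:

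- *Pain is measured only around sessions.* It is not: there are preoperative and 4- to 12-month readings. None of them is within a session, so the gap remains.
- *The VAS is bound to miss cuff pain.* The recall period and the delay after cuff release are unstated. A score taken at once, or one that patients answer for the whole session, could capture some of it. May miss or dilute is as far as the text goes.
- *Cuff discomfort is the one expected side effect.* The protocol calls it a potential risk. It is the only device risk not labelled theoretical, which is a weaker statement.
- *The before and after readings will show a zero excess.* That follows only if complete resolution is assumed, which builds in the answer.
- *Nothing would show why patients stop.* The primary reason for discontinuing the study is to be documented. What is not described is a record for a patient who stays in the study but curtails cuff use.

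Reading a non-significant difference as no difference, without a margin, is a separate weakness that a new pain item would not cure.

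**Conclusion.** The point holds in limited form. By the protocol's own account, device discomfort arises in an interval that no VAS reading covers, so a null before and after comparison says nothing firm about pain during cuff inflation. That conclusion rests on the stated timings alone and needs no assumed figure.

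The size of the loss cannot be fixed from the documents. Over the assumed range for D = 0.9, power at the post-session reading runs from the full 0.79 (20 per group) or 0.88 (25 per group) down to 0.05, according to the share that persists. Effect, SD and persisting share are all assumptions.

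The primary outcome and its analysis are untouched. This is an inexpensive improvement to one secondary outcome, not a flaw that threatens the trial's main result.

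**What to change.** At the existing post-session VAS, add one line, worded identically in both arms: worst pain during today's session. Name it as a secondary outcome, compare it between arms, and state in advance how a patient's repeated readings will be summarised. Limit any no-difference statement drawn from the before and after readings to pain around sessions.

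Do not add a cuff-specific question in the cuff arm alone. Strength, thigh circumference and range of motion are measured at therapy sessions by evaluators who are meant to be blinded. An arm-specific line could reveal allocation on session paperwork, and it would prompt unblinded patients about discomfort unequally.

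The cost is one extra line per session and a short amendment, with no added visit or procedure. The ratings will be unblinded, as the current VAS ratings are. The result may look less favourable to the cuff. Sessions completed before the change cannot be recovered, so the item would cover later sessions only.

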Delfi's PTS Personalized Tourniquet System (Delfi Medical Innovations Inc., Vancouver, Canada), a form of moderated blood flow training, has been used by the Missouri Orthopaedic Institute Department of Physical Therapy for its proven safety and effectiveness in help to promote muscular strength gains, enhance sports performance, and to assist with rehabilitation from injury or surgery.

Moderated blood flow training causes increased blood pooling in the limbs. During exercise lactic acid is then produced. Due to the moderation of blood flow, the lactic acid is retained longer in the muscles. Hypoxia, acidosis, inorganic phosphate, AMP and other local factors have been shown to turn on transcription, and thus, protein synthesis in muscle cells. This local effect results in stimulation of muscle, tendon and vascular growth (5). Muscle receptors also send stronger signals to the brain which in turn causes large quantities of growth hormone to be released. Under the condition of moderated blood flow therapy, it has been shown that even short-term and low-intensity exercise can induce muscle strength, hypertrophy and increasing muscle mass (7-9).

3. Study Statistics

- a. Primary outcome variable will be muscle strength determined by a trained observer blinded to therapy cohort and time point.
- b. Secondary outcome variables will include: thigh circumference, VAS pain scores, IKDC, Tegner, PROMIS surveys, knee range of motion, KT 2000, Lachman exam, lab levels of HGH, IGF, and CK.
- c. Number of patients per group (n=25) was determined from a pre-study power analysis (t-Test) using previously published data on rehabilitation after ACL reconstruction for a desired power of 0.8 and alpha = 0.05. This analysis resulted in recommended sample size of 20 per group. The N of 25 per group was chosen to allow for subjects lost to follow-up.

4. Risks

- a. Patient confidentiality during the course of this study will be protected in compliance with HIPAA requirements as well as the requirements of the University of Missouri Health-Sciences IRB.

After consent is obtained, all subjects will be assigned a study identification number that requires the use of a key in order to decipher a subject's personal identification information. The key will be kept in the Cerner Power Trials database, which is password protected. The study identification number will be used to label all paper data collection instruments.

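### The blinding paragraph calls every remaining outcome objective, but VAS, IKDC, Tegner and PROMIS are self-reports from patients who know their arm

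*Combined protocol and SAP*

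**What the plan says.** Study Procedures, item c, deals with blinding. On patients it states: "Blinding of the subject will not be possible", because they can tell whether the device has been applied and a sham is ruled out. Evaluators are to be blinded "during assessment of muscle strength, thigh circumference, knee range of motion, Lachman exam, and KT2000", and surgeons are blinded too. The paragraph then ends: "All other outcome measures are objective and quantitative".

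Study Statistics, item a, makes muscle strength the primary outcome, measured by an observer blinded to cohort and time point. Item b lists the secondary outcomes: "thigh circumference, VAS pain scores, IKDC, Tegner, PROMIS surveys, knee range of motion, KT 2000, Lachman exam, lab levels of HGH, IGF, and CK".

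Study Procedures, item a, shows who supplies the questionnaire data at baseline: "Patients will also complete preoperative IKDC, Tegner, PROMIS, and VAS pain surveys". For follow-up it says: "The PROMIS, IKDC, and Tegner surveys will be given at 4, 6, 8, 12 month intervals". VAS pain is also taken before and after every therapy session. The opening Hypothesis predicts no significant difference between arms on IKDC, Tegner, PROMIS and VAS.

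**The concern.** A score can be numerical without being objective. When the patient is the rater and knows the arm, a blinded evaluator or surgeon cannot keep knowledge of treatment out of the score. The closing sentence hides this for four outcomes, and no other part of the protocol corrects it or says who is present when the forms are filled in.

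The bias could go either way. The Background and Devices sections describe the technique as safe and effective, and the Benefits section names a potential gain for the treated group, so treated patients may expect to do better. The Risks section names temporary discomfort from the tourniquet during sessions, which could push scores the other way. VAS is collected on either side of the session in which the device is or is not used.

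A false difference on these scores would be read as a treatment effect. A real difference that was cancelled would look like the predicted absence of difference. A reader who accepts the word objective would give either result too much weight.

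**Working it through.** **Step 1. Sort the outcomes.** Study Statistics, items a and b, name 1 primary and 11 secondary outcomes, 12 in all.

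| Group | Outcomes | Count |
|---|---|---|
| Blinded evaluator (Study Procedures, item c) | strength, thigh circumference, range of motion, Lachman, KT2000 | 5 |
| Remaining, laboratory values | HGH, IGF, CK | 3 |
| Remaining, completed by the patient | VAS, IKDC, Tegner, PROMIS | 4 |

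12 − 5 = 7 outcomes fall under the closing sentence. Its description fits 3 of the 7 and fails for 4.

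**Step 2. The plan's own figure.** The only calculated figure is 20 per group (t-test, power 0.8, alpha 0.05), raised to 25 for loss to follow-up. It cannot be reproduced, because no effect size or SD is given. Solved backwards with a two-sided t-test, 20 per group corresponds to a standardised difference of about 0.91. The step to 25 fits 20% loss, since 20 / (1 − 0.20) = 25. The finding does not depend on these figures. They only supply the two values of n used below.

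**Step 3. False differences.** The documents give no size for reporting bias, so the shift b (in SD units) is an assumption and is shown as a range. With no true effect and a two-sided 5% t-test:

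- noncentrality λ = b × √(n/2), degrees of freedom = 2n − 2
- rejection rate = P(|T| > critical t), with T noncentral t
- n = 20: √10 = 3.162, df 38, critical t 2.024
- n = 25: √12.5 = 3.536, df 48, critical t 2.011

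| Assumed shift b (SD) | λ, n = 20 | Rejection, n = 20 | λ, n = 25 | Rejection, n = 25 |
|---|---|---|---|---|
| 0 | 0 | 5.0% | 0 | 5.0% |
| 0.1 | 0.316 | 6.1% | 0.354 | 6.4% |
| 0.2 | 0.632 | 9.5% | 0.707 | 10.7% |
| 0.3 | 0.949 | 15.2% | 1.061 | 18.0% |
| 0.4 | 1.265 | 23.4% | 1.414 | 28.3% |
| 0.5 | 1.581 | 33.8% | 1.768 | 41.0% |

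These are rates for one score at one time point.

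**Step 4. Masked differences.** If the true difference is δ and the shift b runs against it, the test sees δ − b, so the same table applies. As an illustration, take δ = 0.5 and b = 0.3. The net difference is 0.5 − 0.3 = 0.2, and the chance of detection falls from 33.8% to 9.5% with 20 per arm, or from 41.0% to 10.7% with 25. If b = 0.5, the net difference is 0 and the rate is 5%. Cancellation is complete only when the opposing shift is as large as the true difference.

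**The case against.** The strongest reply is that the sentence has no operative role. The reason given for not blinding patients is that they recognise the device and that a sham is impractical. A reader might infer that the plan leaves these outcomes unblinded because it takes them to be objective, but the text does not say so, and no analysis rule rests on the sentence. That stands: what the documents support is that the description is false for four outcomes.

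A reader might also infer that the main result is compromised. The documents do not support that. All four scores are secondary, and strength has a blinded observer.

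Nor does the plan leave these scores with no safeguard of any kind. Blinded surgeons may limit the surgeon's influence at clinic visits. This part of the objection is weaker, because it does nothing about the patient's own expectation.

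It is also fair that the shifts are assumed and that at 0.1 SD the effect is small, at about 6%. Secondary rank already limits what these scores can claim. It does not tell a reader that they are open to reporting bias, however, and the hypothesis makes a specific prediction about each of them.

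**Conclusion.** The sentence is wrong as written for four of the seven outcomes it covers and should be corrected. It is correct for HGH, IGF and CK, and assessment of the primary outcome is untouched.

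The four affected outcomes cannot alone show either benefit or absence of difference. Over the assumed range of 0.1 to 0.5 SD, a pure reporting shift would give a false difference in about 6% to 34% of trials with 20 per arm, or 6% to 41% with 25, against a nominal 5%. These figures assume a two-sided t-test on each score, since the plan does not state sidedness. They illustrate what such a shift would do. They are not evidence that a shift of any given size, or in either direction, will occur in this trial.

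**What to change.** 1. Replace the closing sentence of Study Procedures, item c, with: *HGH, IGF and CK are objective; VAS, IKDC, Tegner and PROMIS are self-reported by unblinded patients.*
2. Keep every survey and VAS time point as scheduled, including the post-session VAS. Have patients complete the forms themselves, on paper or electronically, without the treating therapist. This reduces interviewer influence but does not remove patient expectation.
3. State in Study Statistics, item b, that these four are open-label supportive outcomes that cannot on their own confirm benefit or absence of difference.

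Sample size, alpha and treatment do not change. The cost is weaker claims for the patient-reported outcomes and minor survey logistics. The documents mention the electronic platform only for consent, so its use for surveys should not be assumed. Paper forms would do.
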